6.2.3 Month 2 (\pm 4 days)

- Telephone contact.
- Review and record new concomitant medications.
- Assess symptoms/adverse events and by asking the participants to respond to a non-leading question such as “How have you been feeling?”
- Assess drug compliance with the question “Have you been taking your medication every day as instructed?”

6.2.4 Month 3 (\pm 7 days)

- ADAS-cog, MMSE, CDR, ADCS-ADL, COWAT, CFT and Trail making test (Versions A and B), and NPI.
- C-SSRS.

- Review and record new concomitant medications.
- Assess symptoms/adverse events by asking the participants to respond to a non-leading question such as “How have you been feeling?”
- Brief physical and neurologic examination.
- Body weight.
- ECG.
- Vital signs: blood pressure (supine) and pulse rate.
- Collect blood sample for plasma retention and storage.
- Blood and urine sampling for safety laboratory testing including HbA1c.
- Collect blood samples for PK and PD.
- Drug accountability. Any discrepancies are recorded in the source and the subject and caregiver/informant are counseled regarding proper dosing compliance.
- Dispense study drug. Subjects take their dose of study medication in the clinic.

6.2.5 Month 6 (± 7 days)

- ADAS-cog, MMSE, CDR, ADCS-ADL, COWAT, CFT, Trail making test (Versions A and B), NPI, RUD Lite and DEMQOL- proxy.
- C-SSRS.
- Review and record new concomitant medications.
- Assess symptoms/adverse events and by asking the participants to respond to a non-leading question such as “How have you been feeling?”
- Brief physical and neurologic examination.
- Body weight.
- ECG.
- Vital signs: blood pressure (supine) and pulse rate.
- Collect blood sample for plasma retention and storage.
- Blood and urine sampling for safety laboratory testing including HbA1c.

- Collect blood samples for PK and PD
- Drug accountability. Any discrepancies are recorded in the source and the subject and caregiver/informant are counseled regarding proper dosing compliance.
- Dispense study drug. Subjects take their dose of study medication in the clinic.

6.2.6 Month 9 (\pm 7 days)

- ADAS-cog.
- C-SSRS.
- Review and record new concomitant medications.
- Assess symptoms/adverse events and by asking the participants to respond to a non-leading question such as “How have you been feeling?”
- Brief physical and neurologic examination.
- Body weight.
- ECG.
- Vital signs: blood pressure (supine) and pulse rate.
- Blood and urine sampling for safety laboratory testing including HbA1c.
- Drug accountability. Any discrepancies are recorded in the source and the subject and caregiver/informant are counseled regarding proper dosing compliance
- Dispense study drug. Subjects take their dose of study medication in the clinic.

6.2.7 Month 12 (\pm 7 days)

- ADAS-cog, MMSE, CDR, ADCS-ADL, COWAT, CFT, Trail making test (Versions A and B), NPI, RUD Lite and DEMQOL- proxy.
- C-SSRS.
- Review and record new concomitant medications.

- Assess symptoms/adverse events and by asking the participants to respond to a non-leading question such as “How have you been feeling?”
- Brief physical and neurologic examination.
- Body weight.
- ECG.
- Vital signs: blood pressure (supine) and pulse rate.
- FDG-PET (if applicable)
- Collect blood sample for plasma retention and storage.
- Blood and urine sampling for safety laboratory testing including HbA1c.
- Collect blood samples for PK and PD.
- Drug accountability. Any discrepancies are recorded in the source and the subject and caregiver/informant are counseled regarding proper dosing compliance.
- Dispense study drug. Subjects take their dose of study medication in the clinic.

6.2.8 Month 15 (\pm 7 days)

- ADAS-cog.
- C-SSRS.
- Review and record new concomitant medications.
- Assess symptoms/adverse events and by asking the participants to respond to a non-leading question such as “How have you been feeling?”
- Brief physical and neurologic examination.
- Body weight.
- ECG.
- Vital signs: blood pressure (supine) and pulse rate.
- Blood and urine sampling for safety laboratory testing including HbA1c.

- Drug accountability. Any discrepancies are recorded in the source and the subject and caregiver/informant are counseled regarding proper dosing compliance.
- Dispense study drug. Subjects take their dose of study medication in the clinic.

6.2.9 Month 18 (\pm 7 days)

- ADAS-cog, MMSE, CDR, ADCS-ADL, COWAT, CFT, Trail making test (Versions A and B), NPI, RUD Lite and DEMQOL- proxy.
- C-SSRS.
- Review and record new concomitant medications.
- Assess symptoms/adverse events and by asking the participants to respond to a non-leading question such as “How have you been feeling?”
- Brief physical and neurologic examination.
- Body weight.
- ECG.
- Vital signs: blood pressure (supine) and pulse rate.
- MRI if one was obtained during the screening period. If a CT scan was used for assessing eligibility, then the 18 month MRI scan will not be performed, and the CT scan will not be repeated.
- FDG-PET (if applicable).
- Collect blood sample for plasma retention and storage.
- Blood and urine sampling for safety laboratory testing including HbA1c.
- Collect blood samples for PK and PD.
- Drug accountability. Any discrepancies are recorded in the source and the subject and caregiver/informant are counseled regarding proper dosing compliance.

6.2.10 Follow-Up

A Follow-up Visit should be completed 3 months [± 7 days] after a subject completes Month 18 for those participants who choose not to participate in the open label extension.

A follow-up Visit should be completed 3 months [± 7 days] after the last dose of study drug if the subjects discontinues the study prior to Month 18.

If a subject does not complete a follow up visit, the reason should be documented in the source and EDC.

At any point, if a participant withdraws consent, no further evaluations should be performed, and no additional data should be collected.

- ADAS-cog, MMSE, CDR, ADCS-ADL COWAT, CFT, Trail making test (Versions A and B), and NPI.
- C-SSRS.
- Review and record new concomitant medications.
- Assess symptoms/adverse events and by asking the participants to respond to a non-leading question such as “How have you been feeling?”
- Brief physical and neurologic examination.
- ECG.
- Vital signs: blood pressure (supine) and pulse rate.
- Collect blood sample for plasma retention and storage.
- Blood and urine sampling for safety laboratory testing including HbA1c.
- Collect blood samples for PK and PD.

6.3 EARLY TERMINATION

In the event a subject discontinues participation prior to completion of the Month 18 Visit, the Early Termination Visit should be completed performing the study procedures as follows. A Follow-up Visit should be performed 3 months after the

last dose of study drug. However, if a participant withdraws consent prior to early termination, no further evaluations should be performed, and no additional data should be collected.

- ADAS-cog, MMSE, CDR, ADCS-ADL, COWAT, CFT, Trail Making Tests (Versions A and B), NPI, RUD Lite and DEMQOL- proxy. (These neuropsychological assessments are only performed at the Early Termination visit if within 30 days of the last dose of study drug)
- C-SSRS.
- Review and record new concomitant medications.
- Assess symptoms/adverse events and by asking the participants to respond to a non-leading question such as “How have you been feeling?”
- Brief physical and neurologic examination.
- Body weight.
- ECG.
- Vital signs: blood pressure (supine) and pulse rate.
- MRI if one was obtained during the screening period. If a CT scan was used for assessing eligibility, then this MRI scan will not be performed and a CT scan will not be performed at this visit.
- FDG-PET if participant was on study for ≥ 3 months (if applicable) and if an MRI scan has been performed and passed the central reader’s quality control review. In all cases, it should only be performed if the subject was taking study drug at the time of the PET scan.
- Collect blood sample for plasma retention and storage.
- Blood and urine sampling for safety laboratory testing including HbA1c.
- Collect blood samples for PK and PD.
- Drug accountability. Any discrepancies are recorded in the source.

6.4 SUBJECT WITHDRAWAL

Participants may withdraw from the study at any time at their own request or the request of their study partner, caregiver/informant/guardian, or they may be withdrawn at any time at the discretion of the Investigator or Sponsor for safety, behavioral, compliance, or administrative reasons. If a participant does not return for a scheduled visit, every effort should be made to contact the participant including certified letter, return receipt requested. The investigator should inquire about the reason for withdrawal, request that the participant return all unused investigational product(s), request that the participant return for an Early Termination and Follow-up Visit and follow-up with the participant regarding any unresolved adverse events.

If the participant withdraws from the study, and also withdraws consent for disclosure of future information, no further evaluations should be performed, and no additional data should be collected. The Sponsor may retain and continue to use any data collected before such withdrawal of consent. An individual patient enrolled in the trial may be discontinued from dosing (and continue into the follow-up period) based on a specific adverse event profile as recommended by either the IDMC and/or the Sponsor in discussions with the PI. The IDMC or the Sponsor may temporarily stop dosing of enrolled subjects and/or additional enrollment of new patients at any time, and may permanently terminate the study at any time.

Any emergent medical condition or safety finding that, in the opinion of the Investigator, may jeopardize the participant's safety if he/she continues in the study will be sufficient reason for participant discontinuation from the study. The participant should be followed as indicated for the AE until resolved, declared stable or the participant is lost to follow up. Safety data will be obtained from the physical and neurological examination, vital signs, routine laboratory tests, ECG, brain MRI and neuropsychological testing batteries.

7.0 ASSESSMENTS

7.1 SAFETY AND TOLERABILITY

7.1.1 Vital Signs

Vital signs measurements will consist of blood pressure and pulse rate while the participant is supine. Vital signs will be conducted at all the study visits. Participant should have been supine at least 5 minutes prior to vital signs determination.

7.1.2 Electrocardiogram

12-lead ECG should be recorded after participants have been resting at least 5 minutes in the supine position. Digital ECG tracings will be performed using equipment from and analyzed by a central ECG laboratory. The cardiologist reading the ECGs will be blinded regarding study drug assignment. All standard intervals will be measured.

When assessing eligibility at the Screening visit, the presence of BBB (either left or right) is allowable as long as the absolute QTcF value does not exceed 500 ms and the subject does not have any other cardiac exclusions as described in exclusion criterion 26. When an ECG displays a paced rhythm indicating a functioning pacemaker is present, there is no upper limit as long as there are no related cardiac exclusions (reference exclusion criterion 26). Note. If there is no known history of BBB (either right or left), the discovery of such should prompt further investigation prior to proceeding with screening.

At the Baseline visit, the participant will have an ECG obtained (in triplicate) in order to verify continued eligibility for the study. If the QTcF is >450 msec for males or >470 msec for females is determined based on the average of the 3 QTcFs obtained from the local reading, a subject should not be dosed, pending central reading of the ECG.

When the site receives the Baseline Visit Central ECG Laboratory reading(s), if QTcF is confirmed as exclusionary (using the criteria immediately above), the subject should be excluded. If the central reading does not confirm the exclusion,

the patient may be dosed as soon as convenient/possible. If a patient was dosed based on local reading that determined to be acceptable (using the criteria above) and the central reading is nevertheless determined to be exclusionary, the site should contact the Sponsor for guidance on how to proceed.

At any time during the study, a subject with any of the above ECG values should prompt a call to the Sponsor for guidance on how to proceed.

7.1.3 Physical Examination

Complete physical examination will include skin, eyes, ears, nose and throat, cardiac, respiratory, abdomen, and extremities. Complete physical examination will be conducted at the Screening visit. Brief physical examination will include skin, eyes, oral mucosa, cardiac, and respiratory. A brief physical examination will be conducted at all the study visits. Body weight will be also examined at all study visits.

7.1.4 Neurological Examination

Complete neurological examination will include cortical function, meningeal irritation assessment, cranial nerves, motor and sensory function, coordination, deep tendon reflexes, stance and gait. Complete neurological examination will be conducted at Screening.

Brief neurological examination will include meningeal irritation assessment, cranial nerves, motor and sensory function, coordination, deep tendon reflexes, stance and gait. Brief neurological examination will be conducted at all the study visits.

7.1.5 Laboratory

7.1.5.1 Standard Safety Laboratory Tests

Unless noted otherwise, the following safety laboratory tests will be performed at Screening, Baseline, Month 3, 6, 9, 12, 15, 18, 21 and at time of premature discontinuation. All routine laboratory tests will be analyzed by a central laboratory which will provide instructions and supplies.

Hematology	Chemistry	Urinalysis	Other ^c
Hemoglobin	BUN and Creatinine	pH	FSH ^b
Hematocrit	Glucose	Glucose (qual) Protein	Urine drug screen
RBC count	Calcium	(qual) Blood (qual)	T3, T4, TSH
Platelet count	Sodium	Ketones Nitrites	Vitamin B12
WBC count	Potassium	Leukocyte esterase	Syphilis
MCV	Chloride	Microscopy ^a	Hepatitis B, C
Total neutrophils (Abs)	Total CO2 (Bicarbonate)		
Eosinophils (Abs)	AST		
Monocytes (Abs)	ALT		
Basophils (Abs)	GGT		
Lymphocytes (Abs)	LDH		
	Total Bilirubin		
	Alkaline phosphatase		
	Uric acid		
	Albumin		
	Total protein		
	HbA1c		

a Only if urine dipstick is positive for blood, protein, nitrites or leukocyte esterase.

b Females.

c At screening.

- Hepatitis screens include hepatitis B surface antigen, hepatitis B core antibody, hepatitis B surface antibody, and hepatitis C antibody.
- Minimum requirement for urine drug testing includes: cocaine, THC, opiates, benzodiazepines and amphetamines.

7.1.5.2 Assessment of Potential Cases of Drug Induced Liver Injury

Abnormal values in aspartate transaminase (AST) and/or alanine transaminase (ALT) concurrent with abnormal elevations in total bilirubin that meet the criteria outlined below, in the absence of other causes of liver injury, are considered potential cases of drug-induced liver injury. These events should be considered important medical events, and reported as serious adverse events.

Participants who present with the following laboratory abnormalities should be evaluated further to definitively determine the etiology of the abnormal laboratory values:

- a. Participants with AST or ALT baseline values within the normal range who subsequently present with AST or ALT ≥ 3 times the upper limit of normal concurrent with a total bilirubin ≥ 2 times the upper limit of normal with no evidence of 1) hemolysis, 2) cholestasis (elevated alkaline phosphatase ≥ 2 times the upper limit of normal or not available) or 3) Gilbert's Syndrome (common benign condition associated with intermittent elevations of primarily indirect, unconjugated, bilirubin to about 2 X upper limit of normal.)
- b. Participants with pre-existing AST or ALT baseline values above the normal range who subsequently present with AST or ALT ≥ 2 times the baseline values and ≥ 3 times the upper limit of normal concurrent with a total bilirubin ≥ 2 times the upper limit of normal with no evidence of 1) hemolysis, 2) cholestasis (elevated alkaline phosphatase ≥ 2 times the upper limit of normal or not available) or 3) Gilbert's Syndrome (common benign condition associated with intermittent elevations of primarily indirect, unconjugated, bilirubin to about 2 X upper limit of normal.)

Increases defined above should be confirmed with repeat testing within 48 to 72 hours. In addition to repeating AST and ALT, laboratory tests should include albumin, amylase, creatine kinase, total bilirubin, direct and indirect bilirubin, gamma-glutamyl transferase (GGT), international normalized ratio (INR) and alkaline phosphatase. Symptoms should be assessed. The medical monitor should be contacted to discuss the patient's condition.

Close observation should be immediately initiated if symptoms persist and/or repeat testing confirm the abnormalities described above. Evaluation should include repeating laboratory tests (two or three times weekly; frequency may decrease to once a week or less if abnormalities stabilize or trial drug is discontinued and the subject is asymptomatic), and a detailed medical history and physical assessment. A detailed history, including relevant information, such as history of symptoms or concurrent illnesses, concomitant medication use (including review of acetaminophen use and herbal/dietary supplements), alcohol consumption, recreational drug use and special diets. Additionally family history, sexual history, travel history, history of contact with a jaundiced subject, surgery, blood transfusion, history of liver or allergic disease, and work exposure, should be collected. Ruling out acute hepatitis A, B, C, D, and E infection, autoimmune or alcoholic hepatitis,

NASH, hypoxic/ischemic hepatopathy, Epstein-Barr virus, cytomegalovirus, herpes simplex virus, toxoplasmosis, varicella, parvovirus and biliary tract disease (gall bladder/ductal imaging may be warranted).

All cases confirmed on repeat testing, with no other cause for LFT abnormalities identified at the time should be considered potential drug induced liver injury irrespective of availability of all the results of the investigations performed to determine etiology of the abnormal LFTs.

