8.0 ADVERSE EVENT REPORTING

8.1 ADVERSE EVENTS

An adverse event (AE) is any untoward medical occurrence in a clinical study participant administered a pharmaceutical product. Study drug treatment does not necessarily have a causal relationship with the AE. An AE, therefore, can be any unfavorable change in structure, function or chemistry (including abnormal clinical lab results, or ECG findings), symptoms, signs, or diseases temporally associated with the use of a medicinal (investigational) product, whether or not related to the medicinal (investigational) product, as defined by ICH.

The criteria for determining whether an abnormal objective test finding should be reported as an adverse event are as follows:

- Test result is associated with accompanying symptoms, and/or
- Test result requires additional diagnostic testing or medical/surgical intervention, and/or
- Test result leads to a change in study dosing or discontinuation from the study, significant additional concomitant drug treatment, or other therapy, and/or
- Test result is considered to be an adverse event by the investigator or sponsor.

Repeating an abnormal test, in the absence of any of the above conditions, does not constitute an adverse event. Any abnormal test result that is determined to be an error does not require reporting as an adverse event.

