8.5 SERIOUS ADVERSE EVENTS

A serious adverse event (SAE) is any AE that is fatal or life-threatening (see below), results in persistent or significant disability (see below) or incapacity, requires inpatient hospitalization or prolongation of an existing hospitalization, or is a congenital anomaly/birth defect.

Other important medical events that may not result in death, be life-threatening or require hospitalization should also be considered SAEs when, based upon appropriate medical judgment, they may jeopardize the study participant and may require medical or surgical intervention to prevent one of the outcomes listed above. Examples of such medical events include allergic bronchospasm requiring intensive treatment in an emergency room or at home or convulsions that do not result in inpatient hospitalization.

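### The protocol's liver-injury criteria, on their natural reading, treat a missing alkaline phosphatase result as cholestasis and so exclude the patient

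*Protocol*

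**What the plan says.** Protocol Section 7.1.5.2 opens by saying that transaminase and bilirubin abnormalities meeting the listed criteria, "in the absence of other causes of liver injury, are considered potential cases of drug-induced liver injury", and are to be reported as SAEs. Two criteria follow. Criterion (a), for patients with normal baseline transaminases, needs AST or ALT at least 3 × ULN together with total bilirubin at least 2 × ULN. Criterion (b), for patients whose baseline was already raised, adds that AST or ALT must be at least twice baseline. Both require no evidence of three other explanations: hemolysis, cholestasis and Gilbert's Syndrome. In both, the cholestasis item reads "cholestasis (elevated alkaline phosphatase ≥ 2 times the upper limit of normal or not available".

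The section continues: "Increases defined above should be confirmed with repeat testing within 48 to 72 hours". The repeat panel includes ALP, and the medical monitor is to be contacted. The last paragraph says that cases confirmed on repeat testing, with no other cause found at the time, "should be considered potential drug induced liver injury irrespective of availability of all the results of the investigations performed" to establish etiology.

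ALP is listed in the chemistry panel of Section 7.1.5.1 beside AST, ALT and total bilirubin, and "All routine laboratory tests will be analyzed by a central laboratory". SAP Section 5.4.4 summarizes patients with AST or ALT at least 3 × ULN and bilirubin at least 2 × ULN, with no ALP condition.

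**The concern.** The bracket follows the word cholestasis and explains it. Inside it, an unavailable ALP stands as an alternative to an ALP of at least 2 × ULN. Since cholestasis defeats the criterion, an unknown ALP has the same effect as a high one. That is the wrong way round for a safety trigger: an absent result does not show another cause, and a patient with both transaminase and bilirubin elevations is one the section exists to catch.

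At stake is recognition at the site and its timing. If the criteria are not met, further evaluation and SAE reporting under this section are not required, and the 48 to 72 hour retest and the call to the medical monitor are not clearly required. A site could also attach the reference to availability to the words about evidence and reach the opposite answer. Two sites could therefore handle the same patient differently.

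**Working it through.** No sample size, power or error rate is involved, so the check reads the criterion as a logical rule.

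**Rule as printed, criterion (a):** met = (AST or ALT ≥ 3 × ULN) and (bilirubin ≥ 2 × ULN) and no hemolysis and no cholestasis and no Gilbert's Syndrome, where cholestasis = (ALP ≥ 2 × ULN, or ALP not available). Criterion (b) adds (AST or ALT ≥ 2 × baseline).

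**Applied to a patient with both elevations, no hemolysis and no Gilbert's Syndrome** (for (b), also at least twice baseline):

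| ALP result | As printed, natural reading | Availability attached to evidence | After the fix |
|---|---|---|---|
| below 2 × ULN | met | met | met |
| at least 2 × ULN | not met | not met | not met |
| missing | **not met** | met | met |

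Only the missing-ALP row changes.

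**What depends on that row.**
- *Further evaluation and SAE reporting* are tied to the criteria. SAE reporting also depends on the absence of other causes of liver injury, so it was never fully automatic.
- *The retest* is tied to the increases defined above it. If that means the full criteria, a missing ALP removes the requirement under the natural reading. If it means only the enzyme and bilirubin rises, the retest still applies and would supply the ALP.
- *The closing paragraph* shows that missing results were not meant to rule a case out. It covers only cases already confirmed on repeat testing, so it does not repair the entry criteria.

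**How the situation could arise.** Section 7.1.5.1 schedules safety laboratory tests after baseline at Months 3, 6, 9, 12, 15, 18 and 21. That is 7 panels, and none omits ALP. A missing value would need a lost result, or laboratory data from a non-protocol visit. SAP Section 6.6 foresees such data without naming the analytes.

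**What still catches the patient.**
- Section 8.1 makes an abnormal result an adverse event where the "Test result requires additional diagnostic testing or medical/surgical intervention".
- Section 8.5 says that important medical events "should also be considered SAEs when, based upon appropriate medical judgment, they may jeopardize the study participant".
- Section 8.7 requires follow-up of clinically significant laboratory abnormalities.
- Section 6.4 makes "Any emergent medical condition or safety finding that, in the opinion of the Investigator, may jeopardize the participant's safety" sufficient reason for discontinuation.

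None of these sets a 48 to 72 hour limit.

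**The case against.** The strongest reply is that the governing words ask for no evidence of cholestasis, and a missing test is not evidence, so the patient qualifies. On that view the bracket is awkward but harmless. The retest wording helps this case: a missing ALP is not an increase, so the retest would follow from the enzyme and bilirubin rises alone, and its panel includes ALP. The stated purpose of the evaluation, to establish etiology, also argues against stopping because one test is absent.

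There are further safeguards. Protocol Section 9.6 provides for ongoing review of safety laboratory data, Section 9.12 has the IDMC review all available safety data, and SAP Section 4.2 has medically qualified staff review laboratory listings. Appendix 1 of the protocol and SAP Section 10 list AST or ALT above 3 × ULN as a value of potential clinical concern, whatever the ALP.

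Much of this stands. The alternative reading is possible, the situation should be rare, and such a patient would probably be noticed. But the words about availability sit inside the bracket that explains cholestasis, so the alternative is not what the sentence most naturally says. The other safeguards neither correct the bracket nor impose the short retest window. If the cautious reading is the intended one, the fix simply states it.

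**Conclusion.** The concern holds. As printed, and on the natural reading, criteria (a) and (b) exclude a patient who has the defining transaminase and bilirubin elevations but no ALP result. The reading rests on where the words stand in the sentence. The text does not wholly settle the matter, so confidence is moderate.

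The practical size is small. The documents give no frequency for a missing ALP and none is assumed here; every scheduled panel includes it. General safety rules remain, without the 48 to 72 hour limit. The co-primary endpoints and the SAP Section 5.4.4 liver summary are unaffected. This is an optional correction to an operative patient-safety rule.

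**What to change.** In both (a) and (b), delete the reference to availability, so that the bracket reads: *cholestasis (alkaline phosphatase at or above 2 × ULN)*. Then add one sentence: *A missing alkaline phosphatase result does not exclude a case; it is to be obtained at the 48 to 72 hour repeat test.* The sponsor's safety physicians should confirm that this is the intended rule.

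This can go out in a clarification letter or with the next amendment. The revision history shows a similar edit: Amendment 5 clarified the bilirubin wording in (b) to match (a). No new test is needed, because ALP is already in the repeat panel, and the outcome for any patient with a known ALP does not change. The cost is possibly an occasional extra evaluation or SAE report for a patient whose repeat ALP later points to cholestasis.
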